2. **Variable:** Receiving the second dose of mRNA vaccine (for cohort 1a and 2a) or a booster vaccination (cohort 1b and 2b) and mounting a specific T cell response one month after second dose of vaccine (cohort 1a and 2a) or booster vaccine (cohort 1b and 2b) defined by detection of SARS-CoV-2 specific T-cells by ELISpot assays after stimulation of T-cells with SARS-CoV-2 peptide mix (yes/no)
3. **Treatment of interest:** ofatumumab treatment, which is started either before or after receiving a SARS-CoV-2 mRNA vaccine (initial vaccination cycle or booster vaccine)
4. **Intercurrent events:**
 - a. Vaccination with a non-mRNA vaccine: patients will be excluded from the study
 - b. Failure to receive the second dose of vaccine (for cohort 1a and 2a): patients will be classified as non-responders
 - c. Failure to initiate ofatumumab treatment within six weeks after completion of the vaccination cycle (cohort 1a) or of the booster vaccine (cohort 1b): patients will be excluded from the efficacy analyses
 - d. Failure to complete ofatumumab initiation or interruption of ofatumumab treatment prior to first vaccination (cohort 2a) or prior to booster vaccination (cohort 2b): patients will be excluded from the study
 - e. No valid detection of SARS-CoV-2 specific T-cells: patients will be excluded from the efficacy analyses if they received their second dose of vaccine (cohort 1a and 2a) or booster vaccine (cohort 1b and 2b) and further analyses will be performed to confirm methodical reasons
5. **Summary measure:** n.a., there will be no formal comparison between cohorts. Response rates will only be calculated within each cohort.

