***Booster vaccination is optional can be performed any time after vacc.2. If a booster vaccination is given, an additional unscheduled visit should be performed 1 month after the booster vaccination in order to assess the immune reaction. If this unscheduled visit would be within 2 weeks of the next scheduled visit, the next scheduled visit can be omitted. This only applies for the first and second booster, there won't be any additional visits for potential following boosters.

Cohort 1b and cohort 2b:

PEP: primary endpoint; Vacc.= vaccination with modRNA vaccine;

Vaccination as part of clinical routine and before the study; required number of vaccinations and interval depends on SmPC of respective modRNA vaccines or local regulations provided e.g. by German health authorities.

First booster vaccination as part of clinical routine according to SmPC of respective vaccine or local regulations, e.g. German health authorities. Additional boosters can be performed any time during the study.

* Screening can be performed any time after completion of the initial vaccination cycle (vacc.2). For cohort 2b, ofatumumab treatment has to be initiated at or after screening but at least 4 weeks before booster vaccination

** Ofatumumab initiation doses can be omitted if patient already receives ofatumumab at the time of screening

*** Additional booster vaccination is optional can be performed any time after the first booster. If a second booster vaccination is given, an unscheduled visit should be performed 1 month after the second booster vaccination in order to assess the immune reaction. If this unscheduled visit would be within 2 weeks of the next scheduled visit, the next scheduled visit can be omitted. This only applies for the second booster, there won't be any additional visits for potential following boosters.

The study consists of 2 periods: run-in period and study period.

The **run-in period** comprises the time from screening to vaccination, including the baseline visit (approx. one week before the first vaccination). Patient eligibility will be determined based on the screening and baseline assessments.

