- For cohort 1a, screening and baseline can be performed on the same day, and have to be performed before the first vaccination. Possible effects of the previous MS treatment on vaccination efficacy should be kept in mind when scheduling SARS-CoV-2 vaccination. For cohort 1b, screening and baseline can be performed any time after completion of the initial vaccination cycle and should be approx. 1 week before the first SARS-CoV-2 booster vaccine. Possible effects of the previous MS treatment on booster vaccine efficacy should be kept in mind when scheduling SARS-CoV-2 booster vaccination.
- For cohort 2a and 2b, the run-in period includes initiation of ofatumumab treatment as per approved SmPC and lasts for at least 4 weeks after the first ofatumumab dosing. For cohort 2a and 2b, additional visits during the run-in period will be necessary: one visit to start ofatumumab treatment (can be performed at screening), three remote visits (e.g. phone calls) 1, 2 and 4 weeks after the first ofatumumab dose to ensure the application of the first ofatumumab doses according to SmPC, and the baseline visit approx. 1 week
 - before the first vaccine (cohort 2a).
 - before the first booster vaccination (cohort 2b)

Patients that have already been on stable ofatumumab treatment for at least 4 weeks before the screening visit will follow the run-in period assessment schedule for cohort 1: no additional visits except screening/baseline will be needed. Assessments during the study period will be performed as defined for cohort 2.

The **study period** starts for cohorts 1a and 2a with the first SARS-CoV-2 modRNA vaccination and ends 18 months after the second vaccination (EOS). All patients will return to the study site 1 week, 1 month, 3 months, 6 months, 12 months and 18 months after the second vaccination for study visits. During the study, patients are allowed to receive additional SARS-CoV-2 vaccines (as booster shot or yearly refresher) if suggested by local regulations and as per physician's discretion.

For cohorts 1b and 2b, the study period starts with the first booster vaccination and patients will return to the study site 1 month (equivalates 4 weeks), 3 months, 6 months and 12 months (EOS) after the booster vaccine.

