8.1.2 Information to be collected on screening failures

Participants who sign an informed consent form and subsequently found to be ineligible will be considered a screen failure. The reason for screen failure should be entered on the applicable Case Report Form. The demographic information, informed consent, and Inclusion/Exclusion pages must also be completed for screen failure participants. No other data will be entered into the clinical database for participants who are screen failures, unless the participant experienced a serious adverse event during the screening phase (see SAE section for reporting details).

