9.1 Discontinuation and completion

9.1.1 Study treatment discontinuation and study discontinuation

Discontinuation of study treatment for a participant occurs when study treatment is stopped earlier than the protocol planned duration and can be initiated by either the participant or the investigator.

The investigator must discontinue study treatment for a given participant if, he/she believes that continuation would negatively impact the participant's well-being.

Study treatment must be discontinued under the following circumstances:

- Participant/guardian decision
- Pregnancy
- Use of prohibited treatment as per recommendations in the prohibited treatment section
- Any situation in which study participation might result in a safety risk to the participant

If discontinuation of study treatment occurs, the investigator should make a reasonable effort to understand the primary reason for the participant's premature discontinuation of study treatment and record this information.

Participants who discontinue study treatment or who decide they do not wish to participate in the study further should NOT be considered withdrawn from the study UNLESS they withdraw their consent (see Section 9.1.2 'Withdrawal of Informed Consent' section). **Where possible, they should return for the assessments indicated** in the Assessment Schedule. If they fail to return for these assessments for unknown reasons, every effort (e.g. telephone, e-mail, letter) should be made to contact the participant/pre-designated contact as specified in the lost to follow-up section. This contact should preferably be done according to the study visit schedule.

If the participant cannot or is unwilling to attend any visit(s), the site staff should maintain regular telephone contact with the participant, or with a person pre-designated by the participant. This telephone contact should preferably be done according to the study visit schedule.

After study treatment discontinuation, at a minimum, in abbreviated visits, the following data should be collected at clinic visits or via telephone/email contact:

- New / concomitant treatments
- Adverse Events / Serious Adverse Events (including COVID-19 disease)

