9.1.1.1 Replacement policy

Patients successfully screened who do not receive a SARS-CoV-2 mRNA vaccination or a booster vaccine within 3 months after screening will be excluded from the study and be replaced unless the patient is currently not eligible for SARS-CoV-2 vaccination by local regulation. In this case the Novartis Medical Advisor should be contacted to discuss further proceeding.

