12.1 Analysis sets

For all analysis sets, participants will be analyzed according to the study treatment(s) received.

The safety analysis set will include all participants that received any study drug.

The efficacy analysis sets at one week, one month, six months, 12 months and 18 months after the second SARS-CoV-2 vaccine and 1, 6 and 12 months after a booster vaccine, respectively, will include all participants who have a valid determination of SARS-CoV-2 reactive T-cells at that time point plus those who failed to receive their second dose of vaccine for whatever reason. The latter will be counted as non-responders. Patients completing vaccination but fail to provide a blood sample at one week after the second vaccination will be excluded from the study and analysis.

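### Cohort 2 patients dosed with ofatumumab in the run-in may be excluded from the study or screen-failed under rules that conflict with the protocol's own safety follow-up and safety set

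*Protocol*

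**What the plan says.** **Exposure before vaccination.** Protocol section 3 states that for cohorts 2a and 2b "the run-in period includes initiation of ofatumumab treatment as per approved SmPC" and lasts at least 4 weeks from the first dose. Ofatumumab is supplied by the study (6.1.2). Section 4.5 puts the delay to vaccination at 4 to 12 weeks. Patients already stable on ofatumumab at screening have no initiation run-in.

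**Rules that end participation.**
- Protocol 2.1, item 4d, and SAP 2.5.1, item 4d: if initiation is not completed or treatment is interrupted before the first vaccination (2a) or "prior to booster vaccination (cohort 2b): patients will be excluded from the study".
- Protocol 9.1.1.1: patients not vaccinated "within 3 months after screening will be excluded from the study and be replaced", in either cohort, unless local regulation makes them currently ineligible for vaccination.
- Protocol section 3: "Patient eligibility will be determined based on the screening and baseline assessments". Protocol 8.1.2 then says "No other data will be entered into the clinical database for participants who are screen failures, unless the participant experienced a serious adverse event" in the screening phase. SAP 2.1.1 defines a screening failure by the inclusion and exclusion criteria alone.

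**Rules that keep patients or their data.**
- Protocol 9.1.1: patients who stop study treatment "should NOT be considered withdrawn from the study UNLESS they withdraw their consent". AEs and SAEs, including COVID-19, are still collected.
- Protocol 12.1: "The safety analysis set will include all participants that received any study drug". SAP 2.2 agrees, and SAP 5.2 starts the on-treatment period at the earlier of the first vaccination and the first ofatumumab dose at or after screening.
- Section 8 (final visit with AEs recorded), 10.1.1 (AE monitoring for at least 30 days after the last dose) and 10.1.3 (SAEs from consent to 30 days after the last visit).

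**Nearest cohort 1 event.** Under item 4c, failure to start ofatumumab within six weeks of the vaccination cycle or "of the booster vaccine (cohort 1b): patients will be excluded from the efficacy analyses".

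**The concern.** A site with a cohort 2 patient who stops ofatumumab in the run-in is told by 2.1 that the patient leaves the study and by 9.1.1 that the patient stays and is followed. Both cannot be done. The authors had efficacy-only wording available and used it in item 4c, yet used the stronger wording for the event that concerns patients already dosed.

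The screen-failure rule is a separate problem. It is normally harmless because screening precedes treatment. In cohort 2 part of the eligibility check follows treatment, and nothing in 8.1.2 or SAP 2.1.1 allows for that. The glossary defines a run-in failure, but no later section of the available text uses the term or attaches a data rule to it.

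At stake is the secondary objective on safety and tolerability, with COVID-19 named in the protocol summary as the key safety assessment. Some dosed patients could have shortened follow-up, and some could have no non-serious AE on file while still belonging to the safety set.

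**Working it through.** The point rests on reading the rules against each other; the plan gives no figure for run-in exclusions.

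**Step 1. Is the patient dosed when the rule applies?** Vaccination comes at least 4 weeks after the first dose, and baseline about 1 week before vaccination. Baseline is therefore at least about 4 − 1 = 3 weeks after the first dose. With the 12-week upper end of section 4.5 it is about 12 − 1 = 11 weeks. Cohort 1 starts ofatumumab only after vaccination, so none of these three routes finds a cohort 1 patient with study ofatumumab on board.

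**Step 2. The three routes side by side.**

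| Route | Ends participation | Keeps safety data | Left unresolved |
|---|---|---|---|
| Initiation incomplete or interrupted | 2.1 4d, SAP 2.5.1 4d | 9.1.1, section 8, 10.1.1, 10.1.3, 12.1 | Whether the patient stays in follow-up |
| Not vaccinated within 3 months | 9.1.1.1 | Section 8, 10.1.1, 10.1.3, 12.1 | What happens to AE follow-up of dosed patients |
| Ineligible at baseline after dosing | Section 3 with 8.1.2 and SAP 2.1.1 | SAEs (8.1.2, 10.1.3); safety set membership (12.1) | Non-serious AEs are not entered |

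The conflict is sharpest for a permanent stop, which is how the glossary defines discontinuation. Read literally, a temporary interruption before vaccination removes the patient from the study, while a permanent stop under 9.1.1 does not. For late vaccination, 9.1.1 is silent on a patient who simply continues ofatumumab, so that route conflicts with its purpose more than its letter.

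**Step 3. Safety set.** SAP 5.4 removes patients from the safety set only for a consent violation or for having had no study treatment. Neither item 4d nor 9.1.1.1 appears there, so patients removed by the first two routes remain in the safety set.

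**Step 4. On-treatment window.** It closes 30 days after the last visit (Protocol 12.5.1; SAP 2.9.1 and 5.2). Exclusion in the run-in brings the last visit forward, so the window closes about 30 days later. Otherwise it would run to 30 days beyond month 18 (2a) or month 12 (2b).

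**Step 5. Dosed screen failures.** Under 12.1 and SAP 2.2 they are in the safety set. Under 8.1.2 their non-serious AEs are not entered. Leaving them out breaches the set definition; keeping them in counts them as free of non-serious events.

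**Step 6. Size.** The plan enrols 22 per arm (20 × 1.10 = 22), so one patient is 1/22 = 4.5% of an arm. The documents give no number affected, so k = 1, 2 or 4 is an assumption: 4.5%, 9.1% or 18.2% of starters. If a given non-serious AE has probability q per patient (also assumed), the chance that at least one unrecorded patient had it is 1 − (1 − q)^k:

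| q | k = 1 | k = 2 | k = 4 |
|---|---|---|---|
| 5% | 5% | 10% | 19% |
| 10% | 10% | 19% | 34% |

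**The case against.** The best defence is that the documents, read as a whole, do protect exposed patients. Anyone leaving the study early has a final visit with AEs recorded, AE monitoring runs at least 30 days past the last dose, SAEs are captured on every route, and the safety set takes in everyone dosed. This stands. A reader might infer from item 4d that safety follow-up of these patients is lost outright, or that patients who stop for an AE vanish from the cohort 2 tables. The documents support neither. Stopping for an AE is not an eligibility failure, and such patients stay in the safety set under SAP 2.2 and 5.4.

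The screen-failure route is also narrow. A newly dosed patient must first meet an exclusion criterion at baseline. Current COVID-19 symptoms (exclusion criterion 1) is the clearest example, and the current 9.1.1.1 contains no exclusion for COVID-19 after screening.

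Exclusion of exposed patients is not peculiar to cohort 2 either. The 3-month rule covers both cohorts, and 12.1 excludes fully vaccinated patients in 1a and 2a who lack a week-1 sample. Only the run-in ofatumumab exposure is specific to cohort 2. Item 4c is the nearest event, not a true mirror: it occurs after the vaccination under study, whereas item 4d occurs before it.

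What the defence does not remove is the direct conflict between item 4d and 9.1.1, or the missing exception for dosed patients in 8.1.2 and SAP 2.1.1.

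**Conclusion.** The point holds as two defects in wording and data handling. First, item 4d in both documents contradicts 9.1.1 for patients who stop ofatumumab before vaccination, and 9.1.1.1 does not say what happens to dosed patients it removes. Where exclusion is applied, AE follow-up and the on-treatment window are cut short. Second, non-serious AEs of patients dosed in the run-in and then found ineligible are not entered, while the safety set includes those patients.

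The number affected is unknown and probably small. The primary analysis is not at issue, since these patients are meant to be outside it under either wording. A reader might go further and infer that the safety results are biased in favour of vaccinating on ofatumumab. The documents do not support that: run-in events precede vaccination and describe ofatumumab initiation, much of the safety data is retained, and the safety analysis is descriptive. The point should be corrected, but it does not threaten the trial's main conclusions.

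This rests on a literal reading of 8.1.2 and on at least one new cohort 2 starter having been removed after dosing.

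**What to change.** Reconcile the passages as follows. These are changes to data handling only, not to treatment.

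1. Protocol 2.1 and SAP 2.5.1, item 4d: use the efficacy-only exclusion already in item 4c, and state that patients who received ofatumumab after consent stay in the AE follow-up of 9.1.1 and in the safety set. Add a matching line to SAP 5.4. Without it, a retained patient who is vaccinated later would enter the efficacy set, because 5.4 has no exclusion for this event.
2. Protocol 9.1.1.1: say that such patients are replaced for efficacy, with the same safety follow-up.
3. Protocol 8.1.2 and SAP 2.1.1: limit screen failure to patients with no study treatment after consent, and enter all AEs for anyone dosed.
4. Recruitment ends with the current amendment, so the SAP should state how any dosed patients already excluded or screen-failed are counted in the safety tables, and should report their number.

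The cost is a few sentences in each document, the abbreviated contacts already defined in 9.1.1 for anyone still in follow-up, and entry from source records of any AEs not yet in the database.

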2.2 Secondary estimands

Not applicable

3 Study design

[figure not shown]
This is a two cohort, multicenter, open-label, prospective study of 20 RMS patients per treatment arm (optional increase to 30 depending on results of interim analysis) willing to start ofatumumab treatment and receive SARS-CoV-2 modRNA vaccination (initial vaccination or booster vaccine) as part of clinical routine.

- The first cohort will be RMS patients receiving modRNA vaccine as part of clinical routine prior to starting ofatumumab treatment.
 - Cohort 1a will receive their initial SARS-CoV-2 mRNA vaccines (vaccination 1 and vaccination 2) before starting ofatumumab treatment
 - Cohort 1b will receive a booster vaccination before starting ofatumumab treatment
- The second cohort will be participants receiving modRNA vaccine as part of clinical routine while already stable on ofatumumab treatment for at least 4 weeks (since first dose).
 - Cohort 2a will receive their initial SARS-CoV-2 mRNA vaccines (vaccination 1 and vaccination 2) while being on stable ofatumumab treatment
 - Cohort 2b will receive a booster vaccination while being on stable ofatumumab treatment

Initiation and maintenance of ofatumumab treatment in this study will be performed according to the approved SmPC. Especially for cohort 1, possible effects of the previous MS treatment on vaccination efficacy should be kept in mind when scheduling SARS-CoV-2 vaccination. The interventional part of KYRIOS is limited to the collection of blood samples at specified time-points to analyze development of SARS-CoV-2 specific T-cells and neutralizing antibodies as response to the modRNA vaccination in clinical routine.

Figure 3-1 Study design

Cohort 1a and cohort 2a:

PEP: primary endpoint; Vacc.= vaccination with modRNA vaccine;

Vaccination as part of clinical routine; required number of vaccinations and interval depends on SmPC of respective modRNA vaccines or local regulations provided e.g. by German health authorities.

[figure not shown]
Booster vaccination as part of clinical routine e.g. if suggested by German health authorities and at the physician's discretion.

* Ofatumumab treatment has to be initiated at least 4 weeks before Vacc.1,

** Ofatumumab initiation doses can be omitted if patient already receives ofatumumab at the time of screening

***Booster vaccination is optional can be performed any time after vacc.2. If a booster vaccination is given, an additional unscheduled visit should be performed 1 month after the booster vaccination in order to assess the immune reaction. If this unscheduled visit would be within 2 weeks of the next scheduled visit, the next scheduled visit can be omitted. This only applies for the first and second booster, there won't be any additional visits for potential following boosters.

Cohort 1b and cohort 2b:

PEP: primary endpoint; Vacc.= vaccination with modRNA vaccine;

Vaccination as part of clinical routine and before the study; required number of vaccinations and interval depends on SmPC of respective modRNA vaccines or local regulations provided e.g. by German health authorities.

First booster vaccination as part of clinical routine according to SmPC of respective vaccine or local regulations, e.g. German health authorities. Additional boosters can be performed any time during the study.

* Screening can be performed any time after completion of the initial vaccination cycle (vacc.2). For cohort 2b, ofatumumab treatment has to be initiated at or after screening but at least 4 weeks before booster vaccination

** Ofatumumab initiation doses can be omitted if patient already receives ofatumumab at the time of screening

*** Additional booster vaccination is optional can be performed any time after the first booster. If a second booster vaccination is given, an unscheduled visit should be performed 1 month after the second booster vaccination in order to assess the immune reaction. If this unscheduled visit would be within 2 weeks of the next scheduled visit, the next scheduled visit can be omitted. This only applies for the second booster, there won't be any additional visits for potential following boosters.

The study consists of 2 periods: run-in period and study period.

The **run-in period** comprises the time from screening to vaccination, including the baseline visit (approx. one week before the first vaccination). Patient eligibility will be determined based on the screening and baseline assessments.

- For cohort 1a, screening and baseline can be performed on the same day, and have to be performed before the first vaccination. Possible effects of the previous MS treatment on vaccination efficacy should be kept in mind when scheduling SARS-CoV-2 vaccination. For cohort 1b, screening and baseline can be performed any time after completion of the initial vaccination cycle and should be approx. 1 week before the first SARS-CoV-2 booster vaccine. Possible effects of the previous MS treatment on booster vaccine efficacy should be kept in mind when scheduling SARS-CoV-2 booster vaccination.
- For cohort 2a and 2b, the run-in period includes initiation of ofatumumab treatment as per approved SmPC and lasts for at least 4 weeks after the first ofatumumab dosing. For cohort 2a and 2b, additional visits during the run-in period will be necessary: one visit to start ofatumumab treatment (can be performed at screening), three remote visits (e.g. phone calls) 1, 2 and 4 weeks after the first ofatumumab dose to ensure the application of the first ofatumumab doses according to SmPC, and the baseline visit approx. 1 week
 - before the first vaccine (cohort 2a).
 - before the first booster vaccination (cohort 2b)

Patients that have already been on stable ofatumumab treatment for at least 4 weeks before the screening visit will follow the run-in period assessment schedule for cohort 1: no additional visits except screening/baseline will be needed. Assessments during the study period will be performed as defined for cohort 2.

The **study period** starts for cohorts 1a and 2a with the first SARS-CoV-2 modRNA vaccination and ends 18 months after the second vaccination (EOS). All patients will return to the study site 1 week, 1 month, 3 months, 6 months, 12 months and 18 months after the second vaccination for study visits. During the study, patients are allowed to receive additional SARS-CoV-2 vaccines (as booster shot or yearly refresher) if suggested by local regulations and as per physician's discretion.

For cohorts 1b and 2b, the study period starts with the first booster vaccination and patients will return to the study site 1 month (equivalates 4 weeks), 3 months, 6 months and 12 months (EOS) after the booster vaccine.

- For cohort 1a, ofatumumab treatment will be initiated as per approved SmPC during visit 2 (4 weeks after receiving the second SARS-CoV-2 modRNA vaccine). Ofatumumab treatment can be started earlier if medically indicated but at the earliest two weeks after the second mRNA vaccine. If ofatumumab treatment can't be started 4 weeks after the second vaccine, the Novartis Medical Advisor should be contacted to discuss further proceeding.
- For cohort 1b, ofatumumab treatment will be initiated as per approved SmPC during visit 1 (4 weeks after receiving the first SARS-CoV-2 modRNA booster vaccine). Ofatumumab treatment can be started earlier if medically indicated but at the earliest

two weeks after the booster vaccine. If ofatumumab treatment can't be started 4 weeks after the booster vaccine, the Novartis Medical Advisor should be contacted to discuss further proceeding.

Cohort 1a and 1b will have three additional remote visits (e.g. phone contact) 1 week, 2 weeks and 4 weeks after the initial ofatumumab dosing in order to ensure application of the first ofatumumab doses according to SmPC.

- Cohort 2a will receive both initial vaccinations while continuing on stable ofatumumab treatment.
- Cohort 2b will receive first booster vaccination while continuing on stable ofatumumab treatment.

4 Rationale

